**Table 9.1.4: Schedule of Events – Post-Infusion Follow-Up (Week 33 – Week 52)**

Assessment	Year 1 – Weeks*											
	33 e	34 e	35 e	36	38 e	40	42 e	44	46 e	48	50 e	52
Study Day*	232	239	246	253	267	281	295	309	323	337	351	365
Physical examination a	X e	X e	X e	X								
Weight a				X		X		X		X		X
Assessment of Adverse Events and Concomitant Medications (including review of subject diary for bleeding and FVIII use)	X	X	X	X	X	X	X	X	X	X	X	X
Vital Signs	X e	X e	X e	X								
Blood chemistry, hematology, and coagulation tests b				X				X				X
Urine Tests b				X								X
Liver Tests b	X	X	X	X	X	X	X	X	X	X	X	X
FVIII assays c	X	X	X	X	X	X	X	X	X	X	X	X
AAV5 TAb Assay				X								X
AAV5 TI Assay				X								X
FVIII antibody titer				X				X				X
Exploratory biomarker assessments d				X		X		X		X		X
PBMC Collection (for determination of FVIII and Capsid specific cellular immunity)				X				X				X
VWF:Ag				X								X
TGA Assay d				X		X		X		X		X
PCR of vector DNA in blood, saliva, urine, semen, and stools				X		X		X		X		X
Haemo-QOL-A assessment												X
EQ-5D-5L												X
HAL												X
WPAI+CIQ:HS												X

Assessment	Year 1 – Weeks*											
	33 e	34 e	35 e	36	38 e	40	42 e	44	46 e	48	50 e	52
PROBE											X	

\* Visit windows are  $\pm$  48 hours through Week 36, then  $\pm$ 1 week until Week 52.

a Complete physical examination should be performed at Week 52; brief physical exam may be performed at other study visits. Weight should be recorded at Week 36 and every 4 weeks through Week 52.

b Refer to [Table 9.7.8.2.1](#) for laboratory assessments to be included, and to [Table 9.7.8.3.1](#) for liver tests. LTs may be monitored more or less frequently (and in particular when ALT values are  $\geq$ 1.5x ULN or  $>$  ULN and  $>$  2x baseline value) based on discussion between the Medical Monitor and the Investigator and review of subject data, but LTs will be monitored at least twice weekly during periods when a subject's ALT is  $\geq$  3x ULN. Subjects with ALT  $\geq$  1.5x ULN or  $>$  ULN and  $>$  2x baseline value during the study and either an alternative etiology considered or for further evaluation of the lab abnormality may undergo additional evaluations (eg, imaging studies including MRI or ultrasound, additional blood tests, and/or liver biopsy) at the discretion of the Investigator. Additional testing of FVIII and LTs during any study week may be performed if: (1) the ALT has increased to above ULN or increased by  $>$  10 U/L from prior assessment; (2) Increases in ALT values from prior assessment are accompanied by declines in FVIII activity level; or after a discussion between the Medical Monitor and the Investigator based on a review of subject data. If FVIII levels and/or ALT values are stable over the course of several weeks, assessment of FVIII activity and ALT levels may be adjusted based on discussion between the Medical Monitor and the Investigator.

c Includes FVIII activity level (chromogenic substrate FVIII assay and one-stage clotting FVIII assay), Bethesda assay (with Nijmegen modification) for hFVIII inhibitor level, coagulation exploratory assay, and hFVIII protein assay. If a subject has used FVIII within 72 hours of a measurement day, all efforts should be made to obtain FVIII activity measurements when a 72-hour interval without FVIII use is achieved; the 72-hour wash-out period is only intended for subjects who have achieved FVIII  $\geq$  5 IU/dL at 16 weeks after BMN 270 infusion and who have not resumed FVIII replacement therapy. If FVIII levels are elevated or stable over the course of several weeks, assessment of FVIII activity may be adjusted based on discussion between the Medical Monitor and the Investigator. A D-dimer may be considered under circumstances in which FVIII activity levels are above the normal physiological range and/or if there is a concern for a venous thromboembolism.

d Blood samples will be collected to evaluate biochemical, molecular, cellular, and genetic/genomic aspects relevant to hemophilia A disease, coagulation, and/or AAV gene transfer, and to develop assays used for these evaluations. Subjects may choose to opt out of the exploratory genetic/genomic research being done to study or try to discover genes that are not yet known to be associated with hemophilia A. While exploratory samples will be collected at the time points indicated above, testing of these samples (including those for TGA assay and any other exploratory assessments) will be performed only as deemed necessary by the Sponsor.

e The scheduled visits at Week 33, Week 34, Week 35, Week 38, Week 42, Week 46, and Week 50 may be performed by a mobile nursing (MN) professional at the subject's home or another suitable location (if the subject has given written informed consent to participate in MN visits), or at the site as a shortened lab draw-only visit. The MN service or site will collect blood samples at these visits. For site lab draw-only visits, sites will contact the subject via phone call or e-mail to collect information regarding adverse events, changes to concomitant medications, bleeding episodes, and FVIII use. For MN visits, the service will collect this information. The physical examination and vital signs assessments listed in the Schedule of Events will not be performed at these MN or lab draw-only visits.

Table 9.1.5: Schedule of Events – Post-Infusion Follow-Up (Year 2 – Year 5)

Assessment	Years 2-5*	Year 2*	Years 3-5*	End of Year Visit				ETV
	Q12W	Q4W g	Q6W g	Year 2	Year 3	Year 4	Year 5	
				W104	W156	W208	W260	
Physical examination a	X a						X a	X
Weight a	X a						X a	X
Assessment of Adverse Events and Concomitant Medications (including review of subject diary for bleeding and FVIII use)	X	X	X				X	X
Vital Signs	X						X	X
Blood chemistry, hematology, and coagulation tests b	X b						X b	X
Urine Tests b	X b						X b	X
Liver Tests b	X	X	X				X	X
FVIII assays c	X	X	X				X	X
AAV5 TAb Assay	X						X	X
AAV5 TI Assay	X						X	X
FVIII antibody titer	X						X	X
Exploratory biomarker assessments c	X						X	X
PBMC Collection (for determination of FVIII and Capsid specific cellular immunity)	X						X	X
VWF:Ag	X						X	X
TGA Assay e	X						X	X
PCR of vector DNA in blood, saliva, urine, semen, and stools d	(X) d	(X) d	(X) d				(X) d	(X) d
Haemo-QOL-A assessment	X f						X f	X
EQ-5D-5L	X f						X f	X
HAL	X f						X f	X
WPAI+CIQ:HS	X f						X f	X

Assessment	Years 2-5*	Year 2*	Years 3-5*	End of Year Visit				ETV
	Q12W	Q4W g	Q6W g	Year 2	Year 3	Year 4	Year 5	
Study Week*				W104	W156	W208	W260	
PROBE	X f				X f			X

\* Visit windows are  $\pm$  2 weeks for visits in Years 2-5. At applicable sites, the Q4W (during Year 2) and Q6W (during Years 3-5) assessments may be conducted by a trained mobile nursing (MN) professional at the subject's home or another suitable location, if the subject has given written informed consent to participate in mobile nursing visits. Q12W and End of Year visits during Years 2-5 cannot be done by a MN professional and must be done at the study site.

a Complete physical examination should be performed at the End of Year visits; brief physical exam may be performed at other study visits. Weight should be recorded at the second Q12W visit each year and at every End of Year visit during Years 2-5.

b Refer to [Table 9.7.8.2.1](#) for laboratory assessments to be included, and to [Table 9.7.8.3.1](#) for liver tests. LTs may be monitored more or less frequently (and in particular when ALT values are  $\geq$  1.5x ULN or  $>$  ULN and  $>$  2x baseline value) based on discussion between the Medical Monitor and the Investigator and review of subject data, but LTs will be monitored at least twice weekly during periods when a subject's ALT is  $\geq$  3x ULN. Subjects with ALT  $\geq$  1.5x ULN or  $>$  ULN and  $>$  2x baseline value during the study and either an alternative etiology considered or for further evaluation of the lab abnormality may undergo additional evaluations (eg, imaging studies including MRI or ultrasound, additional blood tests, and/or liver biopsy) at the discretion of the Investigator. Additional testing of FVIII and LTs during any study week may be performed if: (1) the ALT has increased to above ULN or increased by  $>$  10 U/L from prior assessment; (2) Increases in ALT values from prior assessment are accompanied by declines in FVIII activity level; or after a discussion between the Medical Monitor and the Investigator based on a review of subject data. If FVIII levels and/or ALT values are stable over the course of several weeks, assessment of FVIII activity and ALT levels may be adjusted based on discussion between the Medical Monitor and the Investigator. During Years 2-5 of the Post-Infusion Follow-Up period, urine tests and blood, chemistry, and coagulation tests should be performed at the second Q12W visit each year and at every End of Year visit.

c Includes FVIII activity level (chromogenic substrate FVIII assay and one-stage clotting FVIII assay), Bethesda assay (with Nijmegen modification) for hFVIII inhibitor level, coagulation exploratory assay, and hFVIII protein assay. If a subject has used FVIII within 72 hours of a measurement day, all efforts should be made to obtain FVIII activity measurements when a 72-hour interval without FVIII use is achieved; the 72-hour wash-out period is only intended for subjects who have achieved FVIII  $\geq$  5 IU/dL at 16 weeks after BMN 270 infusion and who have not resumed FVIII replacement therapy. If FVIII levels are elevated or stable over the course of several weeks, assessment of FVIII activity may be adjusted based on discussion between the Medical Monitor and the Investigator. A D-dimer may be considered under circumstances in which FVIII activity levels are above the normal physiological range and/or if there is a concern for a venous thromboembolism. If a subject tests positive in the Bethesda assay (with Nijmegen modification) during Years 3-5, a fresh sample should be collected within 4 weeks of the initial visit that had a positive result.

d Sample testing during Long-Term Follow-Up is not required if at least 3 consecutive samples were negative during the Post-Infusion Follow-Up period. Subjects who have not had 3 consecutive negative semen samples by Week 52 should continue to have PCR testing of semen every 4 weeks (during Year 2) or every 6 weeks (during Years 3-5) until 3 consecutive negative samples are documented (or upon consultation between the Investigator and Medical Monitor).

e Blood samples will be collected to evaluate biochemical, molecular, cellular, and genetic/genomic aspects relevant to hemophilia A disease, coagulation, and/or AAV gene transfer, and to develop assays used for these evaluations. Subjects may choose to opt out of the exploratory genetic/genomic research being done to study or try to discover genes that are not yet known to be associated with hemophilia A. While exploratory samples will be collected at the time points indicated above, testing of these samples (including those for TGA assay and any other exploratory assessments) will be performed only as deemed necessary by the Sponsor.

f PRO assessments during Years 2-5 of Long-Term Follow-up should be performed at the second Q12W visit each year and at every End of Year visit.

g Subjects who meet the definition of treatment failure to BMN 270 therapy after Week 52 may omit the Q4W and Q6W visits during Years 2-5, and must attend only the Q12W and End of Year visits. Such subjects following the abbreviated schedule who have not yet cleared vector shedding in all fluids must still provide samples Q4W (during Year 2) or Q6W (during Years 3-5) until vector shedding has been cleared, either by reporting to the site to provide samples or by providing those samples to a MN professional.

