### **9.7.2 Primary Efficacy Variables**

#### **9.7.2.1 FVIII Activity**

The primary efficacy variable is change of the hFVIII activity, as measured by chromogenic substrate assay, during Weeks 49-52 post-BMN 270 infusion from baseline. Each subject's hFVIII activity during Weeks 49-52 is defined as the median of the values obtained during this 4-week window. Values for FVIII activity will be excluded if obtained within 72 hours since the last infusion of exogenous FVIII protein concentrates.

If a subject has used FVIII within 72 hours of a measurement day, all efforts should be made to obtain FVIII activity measurements when a 72-hour interval without FVIII use is achieved; The 72-hour wash-out period is only intended for subjects who have achieved  $FVIII \geq 5$  IU/dL at 16 weeks after BMN 270 infusion and who have not resumed FVIII replacement therapy.

In the event of an FVIII activity level decline during the study:

- If FVIII activity has declined at least 20% from the peak but less than 35% and has declined for at least 2 consecutive assessments, FVIII activity and LTs should be repeated every 7 days until FVIII activity is stable or increasing

- If FVIII activity has declined >35% from the peak and has declined for at least 2 consecutive assessments, FVIII activity and LTs should be repeated every 72 hours until FVIII activity is stable or increasing

Note that fluctuations in FVIII activity are common, and if no clear trend indicating a decline in FVIII activity is observed, then this additional testing may be deferred (upon consultation between the Investigator and the Medical Monitor) until either a more clear trend of decline has been demonstrated or until the FVIII activity levels stabilize or increase.

Subjects who do not respond to BMN 270 treatment [REDACTED]

[REDACTED] may, at the Investigator's discretion and after discussion with the Medical Monitor or Sponsor-designated Data Monitor, follow an abbreviated visit schedule after Week 52 of the study by attending only the Q12W and End of Year visits during Years 2-5.

Details on collecting FVIII activity samples are included in the Laboratory Manual.

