## 12.6 Post-Infusion Follow-Up – Weeks 27-52

During Weeks 27-36, subjects will return to the study site weekly ( $\pm$  48 hours). During Weeks 37-52, subjects will return to the study site every 2 weeks (Week 38, 40, 42, 44, 46, 48, 50, and 52) ( $\pm$  1 week). Optional MN services or shortened lab draw-only site visits may be conducted for the visits at Week 27, Week 29, Week 30, Week 31, Week 33, Week 34, Week 35, Week 38, Week 42, Week 46, and Week 50.

At these visits, the following procedures will be completed:

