### 12.6.1 Every Visit

At every visit (Weeks 27-36, 38, 40, 42, 44, 46, 48, 50, and 52), the following procedures will be performed:

- Physical examination
  - Brief physical examination should be performed at all weeks except Week 26, when a complete physical examination should be performed
  - For visits where a MN service is being used or a lab draw-only site visit is conducted, physical examination will not be performed.
- Assessment of Adverse Events and Concomitant Medications (including review of subject diary for bleeding and FVIII use)
  - For visits where a MN service is being used, the service will contact the subject via e-mail or phone call to collect information regarding adverse events, changes to concomitant medications, bleeding episodes, and FVIII use.
- Vital Signs
  - For visits where a MN service is being used or a lab draw-only site visit is conducted, vital signs will not be performed.
- Liver Tests (refer to [Table 9.7.8.3.1](#))
  - LTs may be monitored more or less frequently (and in particular when ALT values are  $\geq 1.5 \times$  ULN or  $>$  ULN &  $>$  2x baseline value) based on discussion between the Medical Monitor and the Investigator and review of subject data, but LTs will be monitored at least twice weekly during periods when a subject's ALT is  $\geq 3 \times$  ULN.
- FVIII Assays
  - FVIII activity level (chromogenic substrate FVIII assay)
  - FVIII activity level (one-stage clotting FVIII assay)
  - FVIII coagulation activity exploratory assay

- Bethesda assay (with Nijmegen modification) for FVIII inhibitor level
- FVIII protein assay

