### 14.2 Primary Efficacy Endpoint

For the primary efficacy endpoint at Week 52 (ie, the change in the hFVIII activity during Weeks 49-52 post-BMN 270 infusion from baseline, as measured by chromogenic substrate

assay), a one-sample t-test will be used to test the null hypothesis that the change is 0 or less against the alternative hypothesis that the change is greater than 0. Descriptive summaries of the proportions of subjects whose FVIII activity during Weeks 49-52 is greater than or equal to select thresholds, such as 15, 25 and 30 IU/dL, and the confidence intervals of the proportions will also be provided.

For a subject with a missing value of the primary endpoint, the median value in the subject's last 4-week window containing a valid observation will be used. Additional analyses will be conducted to examine the sensitivity of the results to the handling of missing data, including analysis using observed cases, and a mixed model for repeated measures (MMRM) approach. Further detail will be provided in the SAP.

The analyses for the primary endpoint will be performed using the analysis populations as defined in Section 14.8.

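### The Week 50 and Week 52 FVIII draws, the only two scheduled in the primary window, are not exempt from the footnotes that let FVIII sampling be adjusted according to the FVIII level

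*Protocol*

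**What the plan says.** Protocol Section 9.7.2.1 defines the primary value: "Each subject's hFVIII activity during Weeks 49-52 is defined as the median of the values obtained during this 4-week window". It sets no minimum number of values.

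Section 12.6 schedules visits in this period "every 2 weeks (Week 38, 40, 42, 44, 46, 48, 50, and 52", each with a window of plus or minus one week. Weeks 50 and 52 are therefore the only scheduled draws in Weeks 49-52. Section 12.6.1 lists FVIII assays among the procedures for all of these visits: "At every visit (Weeks 27-36, 38, 40, 42, 44, 46, 48, 50, and 52), the following procedures will be performed". It allows a changed frequency for liver tests only.

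Table 9.1.4 covers Weeks 33-52 and is more permissive. Footnote c leaves the decision to the Medical Monitor and the Investigator: "If FVIII levels are elevated or stable over the course of several weeks, assessment of FVIII activity may be adjusted based on discussion between" these two. Footnote b has: "If FVIII levels and/or ALT values are stable over the course of several weeks, assessment of FVIII activity and ALT levels may be adjusted", again after discussion between those two. Neither footnote makes an exception for the primary window.

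Section 9.7.2.1 works in the other direction for a sustained decline. A fall from peak of at least 20% but less than 35% leads to testing every 7 days. For a fall of more than 35%, "FVIII activity and LTs should be repeated every 72 hours until FVIII activity is stable or increasing".

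For a missing primary value, Section 14.2 says that "the median value in the subject's last 4-week window containing a valid observation will be used". Observed-case and MMRM analyses are planned as sensitivity analyses.

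**The concern.** Whether a subject contributes two values, one value or none to the primary window can depend on the FVIII levels that the endpoint measures. The permission to adjust applies to subjects whose level is high or steady, while those in confirmed decline are drawn more often.

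The endpoint definition does not reveal this. A median of one value is treated like a median of two, and a subject with no value is scored on an earlier window. Section 9.7.2.1 requires at least two consecutive declining assessments before it adds draws, so it cannot detect a fall in a subject who is no longer being drawn. If such a fall occurs, the carried value is too high. At stake are the estimated mean change and the descriptive proportions at or above 15, 25 and 30 IU/dL.

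**Working it through.** **1. Which draws are in the window.** Table 9.1.4 puts Week 50 at Day 351 and Week 52 at Day 365. With the one-week visit window, Week 50 is 351 ± 7 = Days 344-358 and Week 52 is 365 ± 7 = Days 358-372. No other draw is scheduled in Weeks 49-52. One omitted draw leaves one value, and two leave none.

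**2. Whether anything protects them.** Section 12.6.1 says that the assays are done at every visit. Footnotes b and c say that they may be adjusted. Nothing says which text prevails. The drafters did set a floor for liver tests in the same footnote b (at least twice weekly while ALT is at or above 3x ULN), but they set none for FVIII.

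**3. The plan's own power figure.** Section 14.7 claims at least 90% power for N = 40, effect size 0.6 and a one-sample t-test at 2-sided 0.05. The noncentral t distribution with df = 39 and noncentrality 0.6 × √40 = 3.79 gives 95.9%, so the claim is reproduced. If subjects without a value were dropped and the effect size stayed at 0.6 (assumption), power would be 90.8% at n = 32 and 89.8% at n = 31. Up to 8 of 40 subjects could be lost before power fell below 90%.

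**4. Carry-forward and the mean.** Let p be the share of subjects with no value in the window and d the relative fall in their activity since the carried window. Each carried value is the true value divided by (1 − d). If these subjects have the same average activity as the rest, the mean is overstated by p × [1/(1 − d) − 1]. Both p and d are assumptions, because the documents give neither.

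| p | d = 0 | d = 5% | d = 10% | d = 20% |
|---|---|---|---|---|
| 10% | 0 | 0.5% | 1.1% | 2.5% |
| 25% | 0 | 1.3% | 2.8% | 6.25% |
| 50% | 0 | 2.6% | 5.6% | 12.5% |

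**5. Carry-forward and the thresholds.** A subject carried at value v is wrongly counted at threshold T only if v(1 − d) < T ≤ v, that is, if v lies from T up to but not including T/(1 − d). At d = 20% the bands are:
- T = 15: 15 to 15/0.8 = 18.75 IU/dL
- T = 25: 25 to 25/0.8 = 31.25 IU/dL
- T = 30: 30 to 30/0.8 = 37.5 IU/dL

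Only subjects carried inside a band are affected, so the proportions may or may not move.

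**6. One value instead of two.** The median of two values is their mean. With independent errors (assumption), one value has twice the within-subject error variance. This costs precision but does not in itself cause bias.

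**7. The observed-case analysis.** If the subjects without a draw were the highest ones (assumption: lognormal activity, median 20 IU/dL, CV 0.6-1.0), the observed-case mean would be 75-85% of the full mean with the top 10% missing, and 58-73% with the top 25% missing. It could therefore err downwards while the primary analysis errs upwards.

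**The case against.** The strongest reply is that adjusted does not mean skipped. The word is undefined. In footnote c the next sentence concerns extra testing at levels above the normal range, so an adjustment for elevated FVIII could mean more draws. Section 12.6.1 says plainly that the assays are done at Weeks 50 and 52. The SAP also describes a data access plan meant to keep people who knew FVIII activity from influencing its collection so as to bias results. These points stand as limits: loss of draws is permitted but not prescribed. They do not remove the gap. Section 12.6.1 conflicts with the footnotes without overriding them. The data access plan, as the SAP describes it, does not mention these draws, and it sits uneasily with footnotes that ask two people to decide on sampling from the FVIII level.

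A second reply is that sampling which depends on FVIII values already observed is missing at random, and a correctly specified MMRM is valid in that setting. This stands in part. MMRM is only a sensitivity analysis, and the primary analysis remains the carried-forward median.

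The documents do not support four stronger readings that a reader might infer:

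- *Only the best responders are affected.* Stable also covers a stable low level.
- *The bias can be sized from the 20% and 35% thresholds in 9.7.2.1.* Those are declines from peak that trigger more sampling. They do not describe drift in subjects judged stable.
- *Every threshold proportion is inflated.* A subject carried at 30 IU/dL after a 20-35% fall is at 24 to 19.5. He is misclassified at 25 and 30 but not at 15.
- *The window closes at Day 365, so a late but compliant Week 52 visit is lost.* No section says this. SAP 19.1 gives Week 50 as Days 344-357 and Week 52 as Days 358-371, together 371 − 344 + 1 = 28 days. Whether that table governs FVIII activity is not stated, and the SAP efficacy text is not in the public copy, so a gap there cannot be assumed.

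**Conclusion.** The point holds as a defect in the written plan. Tables and sections disagree on whether the two draws that make up the primary endpoint can be adjusted, and the permission depends on the outcome. A stable or elevated subject may have one value or none in the window. With none, the carried-forward median overstates the mean change, and possibly the threshold proportions, if activity has since fallen. If it has not fallen, there is no bias.

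The size cannot be derived from the documents. Under the assumed ranges in the table above, the mean is overstated by between 0 and 12.5%. The planned MMRM partly addresses this. Rejection of the null of no increase is little affected, given 95.9% power at the planned size.

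The practical effect on this trial's report is small. The SAP records that one subject was enrolled, that enrollment was terminated and that no summary tables will be produced.

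**What to change.** Add one sentence to footnotes b and c of Table 9.1.4 and to Section 9.7.2.1, for example: *The FVIII activity samples scheduled for Weeks 50 and 52 are taken in every subject and are not subject to adjustment.* Then reconcile Section 12.6.1 with the footnotes, so that it is clear at which other visits, if any, FVIII assays may be adjusted.

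On days, it is enough to confirm that the primary window follows the SAP Week 50 plus Week 52 windows (Days 344-371) and to reconcile the one-day mismatch with the protocol's visit window, which runs to Day 372. Extending the primary window to Day 372 is not recommended. It would make 29 days rather than four weeks and would take a day that SAP 19.1 assigns to Week 56.

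The cost is a few lines of text. Both draws are already scheduled. The downside is that stable subjects lose the option of skipping two draws.
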